#### 7.4 Adverse Event Collection Period

Any AE/SAE prior to the Baseline visit will be considered past medical history (PMH). The AE reporting period for this study begins upon receiving the first application of investigational product and ends at the final protocol required visit. SAE(s) that are observed or spontaneously reported during the subject's participation in the trial will be captured and monitored until the Investigator deems the event to be chronic or not clinically significant or the subject to be stable.

#### 7.5 Adverse Event Reporting

In the event of a SAE, whether related to study drug or not, the Investigator or representative must make an accurate and adequate report consisting of at least the minimum criteria (Site and Subject ID, Date site became aware of the event, SAE Term, Seriousness criteria, Study Drug information, Investigator/Reporter and site address) within 24 hours by email, fax, or telephone to Biorasi Safety and Pharmacovigilance team. Biorasi Safety and Pharmacovigilance team will complete the SAE report onto a MedWatch 3500A form for evaluation and convey for review by the Medical Monitor and Sponsor contact. Accurate Completion of the MedWatch 3500A form will consist of all data supplied such as Subject's demography, SAE narrative, concomitant medication, laboratory parameters and relevant medical history.

In addition, if required by the applicable IRB/IEC, the Investigator will submit the SAE reports to the IRB/IEC within 15 calendar days of discovering the SAE, or alternatively, within accordance of applicable

regulations or IRB/IEC requirements.

Copies of each report with the associated documentation (i.e., queries, medical records, lab records, IRB/IEC communications and all source documents) will be kept in the site's study file.

A subject experiencing one or more SAEs will receive treatment and follow-up evaluations by the Investigator or may be referred to another appropriate physician for treatment and follow-up. The Investigational Site will be responsible for collection and forwarding follow-up SAE information to the Biorasi Safety and Pharmacovigilance.

## **7.6 Unblinding due to SAE**

Treatment assignment for an individual subject should be unblinded only in an emergency by the Investigator, when knowledge of the treatment assignment is urgently needed for the clinical management or welfare of the subject. Treatment should be provided in accordance with the medical condition and with regard to the information provided in the Investigator's Brochure.

The Investigator must document the breaking of the code, and the reasons for doing so on the eCRF, in the site file, and in the medical notes.

The Investigator must notify the Sponsor in writing as soon as possible following the code break detailing the necessity of the code break. Subject always to clinical need and where possible, all other members of the research team should remain blinded.

## 8. DATA ANALYSIS

The sections below summarize the intended statistical methods and analyses of data for the study. A more detailed statistical analysis plan will be written prior to finalization of the clinical trial database. Any changes to the planned methods and analyses will be described and justified in the protocol and/or in the final clinical study report, as appropriate.

Descriptive statistical methods will be used to summarize the data from this study, with confidence intervals calculated for the primary and secondary efficacy endpoints. Unless stated otherwise, the term “descriptive statistics” refers to number of subjects (n), mean, median, standard deviation (SD), minimum, and maximum for continuous data and frequencies and proportions for categorical data. The term “treatment group” refers to randomized treatment assignment: active-test and active-reference. All data collected during the study will be included in data listings. Unless otherwise noted, the data will be sorted first by treatment assignment, subject number, and then by date within each subject number.

Unless specified otherwise, all statistical testing will be two-sided and will be performed using a significance (alpha) level of 0.05.

All statistical analyses will be conducted with the SAS® System, version 9.1.3 or higher.

### 8.1 Subject Population/Data Sets to Be Evaluated

The subject populations are defined as follows:

1. **Safety Population:** The safety population is any randomized individual who (a) was enrolled into the study, and (b) received at least one dose of study treatment.
2. **Modified Intent-to-Treat (mITT) Population:** A modified intent-to-treat subject is any randomized individual who (a) met inclusion/exclusion criteria, (b) was enrolled into the study, (c) received at least one dose of the assigned study treatment, and (c) had at least one post-baseline visit.
3. **Per Protocol (PP) Population:** A per-protocol subject is any randomized individual who (a) met inclusion/exclusion criteria, (b) was enrolled into the study, (c) received the assigned study treatment, (d) had not taken any concomitant medications prohibited by the protocol or experienced any major deviations that interfered with or may have interfered with the therapeutic administration of the treatment or the precise evaluation of treatment efficacy, and (e) completed the primary endpoint evaluation within the designated visit window ( $\pm 4$  days).

Subjects whose condition worsens and require alternate or supplemental therapy for the treatment of scabies during the study will be discontinued, included in both the mITT and PP population analyses as treatment failures. Subjects who discontinue early for reasons other than treatment failure will be excluded from the PP population, but included in the mITT population, using Last Observation Carried Forward (LOCF).

Efficacy analyses will be performed using the per-protocol population as definitive and the mITT population as supportive. Safety analyses will be performed using the Safety population.

## 8.2 Sample Size Determination

Under the assumption that the Reference product has a cure rate of at least 88%, sample size evaluations were conducted, via computer simulation, to determine the probability (power) of the calculated 90% continuity-corrected confidence interval on the Test-to-Reference difference in cure proportions to be contained in the bioequivalence interval [-0.20, +0.20]. When the Test product was assumed to have the same 88% cure rate, the required number of PP subjects in each treatment group was determined to be 56 (112 total) for a power  $\geq 0.80$ . Allowing for up to 20% of the subjects to not qualify for the PP population, 70 subjects in each treatment group (140 total) would be needed.

If it is assumed that the Test product cure rate might deviate from that of the Reference by as much as 2% (e.g. 86% instead of 88%) and if a higher power,  $\geq 0.95$ , was desired, then 91 PP subjects in each treatment group (182 total) would be needed. To allow for up to 20% of the subjects to not qualify for the PP population, 114 subjects in each treatment group (228 total) would need to be enrolled.

## 8.3 Statistical Analyses

### 8.3.1 Subject Disposition and Demography

Descriptive statistics will be generated by treatment group for selected continuous variables. The number and percentage of subjects in each class of categorical demographic and Baseline variables (e.g., gender, ethnicity, and race) will be tabulated by treatment group. Individual subject demographic and Baseline characteristic data will be listed.

### 8.3.2 Assessment of Bioequivalence as Primary and Secondary Endpoints

Bioequivalence assessment will be evaluated by comparing proportions of patients cured in the test and the reference treatment groups. Bioequivalence between the test and the reference product will be established if the 90% confidence interval for the difference in proportions cured between test and reference treatment is contained within the equivalence limits [-0.20, +0.20].

In this case, the compound hypothesis to be tested is:

$H_0: p_T - p_R < -0.20$  or  $p_T - p_R > 0.20$  (meaning test product is not bioequivalent to the reference);

$H_A: -0.20 \leq p_T - p_R \leq 0.20$  (supporting bioequivalence);

where  $p_T$  = cure rate of test treatment,  $p_R$  = cure rate of reference treatment.

Let  $n_T$  = sample size of test treatment group,  $n_R$  = sample size of reference treatment group and

$$se = \left( \widehat{p}_T (1 - \widehat{p}_T) / n_T + \widehat{p}_R (1 - \widehat{p}_R) / n_R \right)^{\frac{1}{2}}.$$

The 90% confidence interval will be estimated as follows, using Yates correction:

$$L = (\hat{p}_T - \hat{p}_R) - 1.645 \times se - \left(\frac{1}{n_T} + \frac{1}{n_R}\right)/2$$

$$U = (\hat{p}_T - \hat{p}_R) + 1.645 \times se + \left(\frac{1}{n_T} + \frac{1}{n_R}\right)/2$$

$H_0$  is rejected if  $L \geq -0.20$  and  $U \leq 0.20$  resulting in accepting  $H_A$  and concluding bioequivalence of the two products.

The primary endpoint is the evaluation at Day 28. The results in the PP population will be considered definitive, with those in the mITT population as supportive.

As a secondary endpoint evaluation, patients' clinical progress at visit 4 (Day 14) will be assessed and proportion of cured patients in each of the treatment arms will be compared using the procedure above.

### **8.3.3 Assessment of retreatment**

Proportion of subjects requiring retreatment in each of the treatment groups will be compared descriptively.

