## PROTOCOL SYNOPSIS

Sponsor: Mayne Pharma, Inc.	Name of Finished Product: Permethrin Cream	Name of Active Ingredient(s): Permethrin, 5%
Study Title A Multi-Center, Double-Blind, Randomized, Parallel-Group Study Comparing Permethrin Cream, 5% (Mayne Pharma, Inc.) with Elimite™ in patients with active scabies.		
Type of Study Bioequivalence with Clinical Endpoints.		
Objectives Primary: To demonstrate bioequivalence between Permethrin Cream, 5% (Mayne Pharma, Inc.) and Elimite™ in patients with active scabies. Secondary: To demonstrate comparative safety of Permethrin Cream, 5% (Mayne Pharma, Inc.) vs Elimite™ and tolerability of Permethrin Cream, 5%.		
Methodology This is a multi-center, double-blind, randomized, two arm parallel design study. This study is comprised of two phases: screening and treatment. The screening period will be up to 5 days, followed by the treatment phase of 28±4 days. During the treatment phase subjects will be randomized to receive either test or reference treatments in a double-blind manner in an outpatient setting. Randomization of subjects will be in a 1:1 ratio for the test and reference drug arms and will be stratified by site. Screening will begin at visit 1, during which eligibility will be determined and prohibited treatments will be discontinued. Randomization will occur following the confirmation of the eligibility criteria at visit 2 (baseline, Day 1) i.e. initiation of treatment phase. The treatment phase will be 28±4 days in duration wherein subject will receive treatment with investigational product (either test or reference) on Day 1 or Baseline (visit 2). Safety and tolerability assessments will be performed on Day 7 (visit 3). Efficacy, safety and tolerability will be assessed on Day 14 (visit 4) followed by the End of study visit on Day 28 (visit 5). If positive identification of scabies is confirmed at Day 14 (visit 4), the subject will be retreated with the second application of the investigational product.		
Planned Number of Subjects Number of subjects to be allocated to treatments according to a 1:1 randomization will depend on the limited availability of Reference product. Currently, enough drug is available for a total of N=140 (enrolled subjects) to achieve N=112 per protocol population. Should additional Reference product become available prior to completion of the clinical phase of the study, enrollment will be increased		

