## 3. INVESTIGATIONAL PLAN

### 3.1 Study Design

This is a multi-center, double-blind, randomized, two-arm parallel design study to compare the treatment success of the test product, Permethrin Cream, 5% (Mayne Pharma, Inc.), and the Reference product, Elimite™ in patients with active scabies. The diagnosis of scabies is made based on the evaluation of burrows, inflammatory papules and excoriations and with a typical distribution pattern and localization (webbed spaces of the fingers, flexor surfaces of the wrists, elbows, axillae, belt line, feet, skin surface of external genitalia, or areolae), presence of family or contacts with moderate to severe itching which increases during the night, and positive identification of mites, mite eggs, or mite fecal matter (scybala) via microscopic evaluation of skin lesion scrapings [1,2]. Treatment success in this study is based on previously published studies of scabies infestations and defined as the absence of new lesions and the healing of all old lesions due to scabies mites and eggs within the treatment area [5-7]. The assigned investigational product will be applied topically (after washing) preferably in the evening on the day of the Baseline visit (Day 1).

Eligibility criteria requires that all regular bedmates and family members with prolonged physical contact with the subject will agree to be assessed by the Investigator for clinical signs of scabies infestation and receive treatment with standard of care scabicide drug, if necessary. This requirement is detailed in Section 5.8.2.

If signs of active scabies infestation are present at visit 4 (Day 14±2), the study subject will be retreated with a second application of their assigned IP. Household members of the participating study subject will be asked to reapply the standard of care generic Permethrin Cream, 5% at the same visit.

This study is comprised of two phases: screening and treatment. The screening phase will be up to 5 days in duration and treatment phase will be 28±4 days in duration. Approximately 140 subjects (or as many as 228 subjects), at least 12 years of age, male or female, of any race, who meet the inclusion and exclusion criteria, will be enrolled to achieve the desired per protocol subject number. The double-blind randomization of subjects will be in a 1:1 ratio for Test and Reference, and will be stratified by site.

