## VISIT 4: INTERIM (DAY 14)

VISIT DATE AT CLINIC:

D	D	M	M	M	Y	Y	Y	Y	

Does the subject require second Application of the Study Drug?  Yes  No

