3.2. Randomization

The actual treatment given to individual subjects is determined by a computerized block randomization scheme prepared by an independent third party. The independent third party will prepare the randomization list and hold it throughout the conduct of the study. The content of the randomization list will not be available to either clinical sites or sponsor up until the database is locked. Subjects are randomized on a 1:1 basis (test drug: active comparator) in blocks of two and stratified by clinical site. The subject randomization number corresponds to either one of the active drugs treatment allocation.

Clinical sites will contact the independent third party responsible for the randomization scheme at the time subject has met all inclusion criteria and is ready for enrollment. Blocks of two (2) tubes will be supplied to the sites. Site's dispensing pharmacist will randomly select a tube with an

investigational product from the block for the study subject. Next enrolled subject will receive the remaining investigational product from the same block until the block is entirely used. Subject eligibility is established before treatment randomization at Visit 2 (Screening and Visit 2 Randomization can be combined into one visit). Subjects are randomized strictly sequentially, as subjects are eligible at the clinical sites.

After signing the Informed Consent, each subject will be assigned a unique subject number. Subjects are identified using subject initials, subject number, and date of birth. The subject numbers will be generated by the EDC and assigned sequentially in the order in which subjects are consented at each center.

If a subject discontinues from the study, the subject number and randomization number are not to be reused, and the subject is not allowed to re-enter the study.

Based on the clinical judgement and requirements described in the protocol, the Investigator may provide a retreatment to the study subject. Only one retreatment is allowed per subject. The retreatment assignment must belong to the same treatment arm. In order to dispense the correct treatment, the following process is to be followed:

1. Study pharmacist will contact the Drug Depot, specifying subject's identifying information.
2. Drug Depot will specify which kit number shall be dispensed for retreatment.

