5.2.4. Secondary Efficacy Analyses

As a secondary endpoint evaluation, patients' clinical progress at Visit 4 (Day 14) will be assessed and proportion of cured patients in treatment arms will be compared using the procedure described

in the analysis of the primary efficacy endpoint.

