6. CHANGES IN THE PLANNED ANALYSES

No deviations in the conduct of the study or the planned analysis are anticipated. Should any deviations from the analyses specified in the authorized statistical analysis plan arise, such deviations will be documented in the final clinical study report.

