8. TABLES, LISTINGS AND FIGURES

Tables

1. Summary of Subject Enrollment and Disposition.
2. Summary of Subject Demographics at Screening (mITT population).
3. Summary of Subject Demographics at Screening (PP Population).
4. Summary of Medical History/Other Concomitant Illness at Screening.
5. Summary of Physical Exam Abnormalities.
6. The proportion of patients that are identified as cured on Study Day 28 (Visit 5) (mITT population).
7. The proportion of patients that are identified as cured on Study Day 28 (Visit 5) visit (PP population).
8. Summary of Visual examination at each visit (mITT population).
9. Summary of Visual examination at each visit (PP Population).
10. The proportion of patients that are identified as cured on Study Day 14 (mITT population).
11. The proportion of patients that are identified as cured on Study Day 14 (PP population).
12. Summary of self-assessment of itching and stinging/ burning sensations at each visit (mITT population).
13. Summary of self-assessment of itching and stinging/ burning sensations at each visit (PP population).
14. Summary of change of self-assessment of itching and stinging/ burning sensations from baseline at each visit (mITT population).
15. Summary of change of self-assessment of itching and stinging/ burning sensations from baseline at each visit (PP population).
16. Adverse Events by System Organ Class and Preferred Term.
17. Adverse Events with incidence >5 % by System Organ Class and Preferred Term.
18. Treatment Emergent Adverse Events by System Organ Class and Preferred Term.
19. Treatment Emergent Adverse Events by maximum Severity.
20. Summary of Treatment Emergent Adverse Events possible or probably related to the study drug.
21. Summary of Serious Adverse Events by System Organ Class and Preferred Term.
22. Summary of Concomitant Medications.

Data Listings

1. Listing of Analysis Population and Study Completion.
2. Listing of Subjects Who Discontinued.
3. Listing of Patients Excluded from Per Protocol Efficacy Analysis.
4. Listing of Protocol Deviation.
5. Listing of Subject Demographics.
6. Listing of Drug Accountability.
7. Listing of Visual Examination.
8. Listing of Subject Diary data.
9. Listing of Patient Self-assessment.
10. Listing of Adverse Events.
11. Listing of Treatment Emergent Adverse Events.
12. Listing of Non-Treatment Emergent Adverse Events.
13. Listing of Adverse drug reaction.

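### Does the SAP's silence on the retreatment proportion planned in Protocol 8.3.3 require a change to the plan?

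*Protocol*

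**What the plan says.** Protocol 8.3.3 is a single sentence: "Proportion of subjects requiring retreatment in each of the treatment groups will be compared descriptively". It sets no population, interval or threshold, and no decision rests on the result.

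The SAP mentions retreatment in three places, always as conduct: the overview (1.1), footnote 7 to Table 1.2, and the dispensing process in 3.2, where "Only one retreatment is allowed per subject". Sections 5.1 to 5.4 contain no retreatment analysis, and no title in section 8 refers to it. Section 6 states: "No deviations in the conduct of the study or the planned analysis are anticipated".

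The underlying data are collected. The Visit 4 page of the Subject Diary (Protocol Appendix C) asks "Does the subject require second Application of the Study Drug", and SAP section 8 includes a "Listing of Subject Diary data". For the secondary endpoint at Day 14, SAP 5.2.4 says that the "proportion of cured patients in treatment arms will be compared using the procedure described" for the primary endpoint.

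The retreatment trigger is worded in two ways. The Protocol Synopsis has "If positive identification of scabies is confirmed at Day 14 (visit 4), the subject will be retreated"; Protocol 3.1 has "If signs of active scabies infestation are present at visit 4".

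**The concern.** A SAP is expected to carry out every analysis that the protocol names, or to say why one is dropped. Here a numbered protocol analysis disappears without comment. If programmers work only from the SAP, the result may never be produced. SAP section 6 would not catch this, because it promises to document departures from the SAP, and an analysis that is absent from the SAP is not a departure from it.

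The subject matter adds weight. The primary endpoint is cure at Day 28, after any second application at Day 14. Similar Day 28 cure in the two arms could in principle be reached with unequal use of second applications, and the retreated proportion by arm shows this directly. The two wordings of the trigger also raise the question of which subjects that proportion counts.

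**Working it through.** The claim is about an omission and depends on no rate, so the main check sets the texts side by side.

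1. **Is the analysis missing from the SAP?** Yes. No subsection of SAP section 5 specifies it, and 0 of 22 tables, 0 of 26 listings and 0 of 6 figures are named for it.

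2. **Does a missing title mean a missing result?** Not reliably, because the section 8 list is not exhaustive. SAP 5.1 promises a by-arm summary of therapy compliance and SAP 5.4 a by-arm summary of vital signs. Neither has a table in section 8; vital signs appear only as Listing 25. The silence of section 5 is the better evidence.

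3. **Has the analysis been cancelled?** No. Protocol section 8 requires changes to planned analyses to be described and justified in the protocol or the study report. No such change is recorded, so 8.3.3 still applies.

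4. **Can it be produced from planned data?** Yes. The diary cover page and Visit 4 page record whether a second application is required, and the page is kept when the answer is no. Accountability logs are completed at dispensing (Protocol 6.3.4) and on return (6.3.5). Listings 6 and 8 carry accountability and diary data by subject. SAP section 7 sorts listings by treatment group (section 5 gives subject order), so counts by arm can be taken from them.

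5. **Does a planned output already carry the main information?** Largely. Day 14 cure precedes any second application and is compared by arm in both the PP and mITT populations (Tables 10 and 11). It is not the exact complement of retreatment. Cure requires all old lesions to have healed, whereas Protocol 6.2.2.1 plans a Visit 4 scraping only for new lesions. A subject with only unhealed old lesions is therefore not cured, yet has no planned test that could give a positive identification.

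6. **How informative could the summary be?** The documents give no retreatment rate. As an assumption, take the same proportion p retreated in both arms, between 12% and 35%. The 90% half-width under the Protocol 8.3.2 formula is 1.645 × √(2p(1−p)/n) + 1/n.
   - n = 56: p = 0.12 gives 0.101 + 0.018 = 0.119; p = 0.35 gives 0.148 + 0.018 = 0.166.
   - n = 91: p = 0.12 gives 0.079 + 0.011 = 0.090; p = 0.35 gives 0.116 + 0.011 = 0.127.

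   So the difference would be known only to within about 9 to 17 points. It gives context and could not be decisive.

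7. **Does the trigger wording alter an analysis?** None is shown to change. Protocol 3.1, 5.8.1 and 6.3.4 and SAP 1.1 all refer to signs of active disease; the Synopsis alone refers to positive identification, which can be read as a subset of such signs. Protocol 5.6.1 applies clinical judgement together with the protocol's requirements, so it is not a third rule. Investigators are blinded, and the descriptive count records what was done. The wordings must be reconciled; that is an editorial matter, and no wording is proposed here.

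**The case for a change.** The strongest contrary case is that this is a plain mismatch, cheap to repair, on a quantity that bears on how the Day 28 result is read. Listings are not summaries, compliance is a different quantity, and Day 14 cure is not one minus the proportion retreated. Nothing in the SAP prompts the analyst to return to 8.3.3. All of that is correct, and adding a line to the SAP would do no harm.

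It does not establish a gain. The protocol already obliges the sponsor to report the proportion, so a SAP line would repeat an existing commitment. Day 28 cure split by retreatment status would go beyond it: 8.3.3 does not ask for that table, and it would divide subjects by a post-randomization event.

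Two related points are also only matters of wording. The cure definition in Protocol 2.2.1 and SAP 5.2.1 has no exception for retreated subjects, so one healed at Day 28 counts as cured. SAP 5.2.3 labels Day 14 as the close of treatment, but the same sentence names the day and visit, so the endpoint is not in doubt.

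**Conclusion.** The omission is real, but it is a small gap that analysts can fill sensibly: one descriptive count and percentage per arm, from data already collected, under a protocol section that still applies. It affects none of the Day 28 test, the ±0.20 limits, the 112 or 182 per-protocol subjects, or the bioequivalence conclusion.

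This rests on two readings: that Protocol section 8 keeps 8.3.3 in force unless a change is justified, and that Listings 6 and 8 include second applications, as the diary and accountability procedures indicate. The precision figures use assumed retreatment rates of 12% to 35%, and the conclusion does not depend on them. No change to the plan follows.
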